6.3. Secondary Efficacy Endpoints

6.3.1. Definition of the Secondary Efficacy Endpoints

The key secondary efficacy endpoints are:

- The proportion of subjects with Endoscopic Response at Week 10
- The proportion of subjects with MCS Response at Week 10
- The proportion of subjects with MCS Remission at Week 10
- The proportion of subjects with Histologic Remission at Week 10

6.3.2. Analysis of the Secondary Efficacy Endpoint

Due to limited subject enrollment in the study, the summary of secondary efficacy endpoints will not be provided. No statistical testing will be performed. A by-subject listing of response status will be provided for the following secondary efficacy endpoints:

- Endoscopic Response (yes, no) at Week 10
- MCS Response (yes, no) at Week 10
- MCS Remission (yes, no) at Week 10

Histologic data will not be read or processed. Consequently, Histologic Remission (yes, no) at Week 10 will not be listed.

CCI

7. SAFETY ANALYSES

7.1. Adverse Events and Deaths

If an AE occurred in Blinded Treatment phase, this AE will be summarized under blinded treatment group. For subjects who entered OL Treatment phase, an AE will be summarized under OL treatment if this AE start date is on or after the first dose of OL treatment.

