7.2.2. Assessment of Severity

The severity of AEs will be graded using the modified Common Terminology Criteria for Adverse Events (CTCAE), Version 5.0 (Appendix 6). For each episode, the highest grade attained should be reported.

If a CTCAE criterion does not exist, the investigator should use the grade or adjectives: Grade 1 (mild), Grade 2 (moderate), Grade 3 (severe), Grade 4 (life-threatening) or Grade 5 (fatal) to describe the maximum intensity of the AE. For purposes of consistency with the CTCAE, these intensity grades are defined in Table 7-1.

Table 7-1. Grading of Adverse Event Severity

Grade	Adjective	Description
Grade 1	Mild	Asymptomatic or mild symptoms; clinical or diagnostic observations only; intervention not indicated
Grade 2	Moderate	Local or noninvasive intervention indicated; limiting age-appropriate instrumental ADL
Grade 3	Severe	Severe or medically significant but not immediately life-threatening; hospitalization or prolongation of hospitalization indicated; disabling; limiting self-care ADL
Grade 4	Life-threatening	Urgent intervention indicated
Grade 5	Death	Death related AE

* Activities of Daily Living (ADL) Instrumental ADL refer to opening preparing meals, shopping for groceries or clothes, using the telephone, managing money, etc.

** Self care ADL refer to bathing, dressing and undressing, feeding self, using the toilet, taking medications, and not bedridden

7.3. Investigator Requirements and Instructions for Reporting Adverse Events and Serious Adverse Events to Gilead

After informed consent, but prior to initiation of study medication, the following types of events should be reported on the CRF/eCRF: all SAEs and AEs related to protocol-mandated procedures.

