7.1.5. Treatment-Emergent Adverse Events

7.1.5.1. Definition of Treatment-Emergent Adverse Events

Treatment-emergent adverse events (TEAEs) for the Blinded Treatment phase are defined as 1 or both of the following:

- Any AEs with an onset date on or after the Blinded Treatment phase study drug start date and no later than 30 days after permanent discontinuation of the Blinded Treatment phase study drug if no OL Treatment phase study drug was taken, OR any AEs with an onset date on or after the Blinded Treatment phase study drug start date and before the OL Treatment phase study drug start date if OL Treatment phase study drug was taken.
- Any AEs leading to premature discontinuation of Blinded Treatment phase study drug.

TEAEs for the OL Treatment phase are defined as 1 or both of the following:

- Any AEs with an onset date on or after the OL Treatment phase study drug start date and no later than 30 days after permanent discontinuation of the OL Treatment phase study drug.
- Any AEs leading to premature discontinuation of OL Treatment phase study drug.

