7.1.6.1. Summaries of AE Incidence in Combined Severity Grade Subsets

A brief, high-level summary of the number and percentage of subjects who experienced at least 1 TEAE in the categories described below will be provided by treatment group. All deaths observed in the study will also be included in this summary.

- TEAE
- TEAEs with Grade 3 or higher
- TEAEs with Grade 2 or higher
- TE treatment-related AEs
- TE treatment-related AEs with Grade 3 or higher
- TE SAEs
- TE treatment-related SAEs
- TEAEs leading to premature discontinuation of study drug

The number and percentage of subjects who experienced at least 1 TEAE will be provided and summarized by PT and treatment group. For the other AE categories described below, summaries will be provided by SOC, PT, and treatment group:

- TE treatment-related AEs
- TE SAEs
- TEAEs leading to premature discontinuation of study drug

Multiple events will be counted only once per subject in each summary. Adverse events will be summarized and listed first in alphabetic order of SOC within each SOC (if applicable), and then by PT in descending order of total frequency within each SOC. For summaries by severity grade, the most severe grade will be used for those AEs that occurred more than once in an individual subject during the study.

Data listings will be provided for the following:

- All AEs, indicating whether the event is treatment emergent
- All SAEs
- All Deaths
- All AEs leading to premature discontinuation of study drug

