7.2.2.1. Treatment-Emergent Laboratory Abnormalities

Treatment-emergent laboratory abnormalities for Blinded Treatment phase are defined as values that increase at least 1 toxicity grade from baseline at any postbaseline time point,

- up to and including the date of last dose of Blinded Treatment phase study drug plus 30 days for subjects who permanently discontinued Blinded Treatment phase study drug
- or before the first dose of OL Treatment phase study drug for subjects who entered OL Treatment phase

For subjects who entered the OL Treatment phase, treatment-emergent laboratory abnormalities for OL Treatment phase are defined as values that increase at least 1 toxicity grade from OL baseline at any postbaseline time point, up to and including the date of last dose of OL Treatment phase study drug plus 30 days for subjects who permanently discontinued OL phase study drug.

If the relevant baseline laboratory value is missing, any abnormality of at least Grade 1 observed within the time frame specified above will be considered treatment emergent.

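### SAP 7.1 and 7.1.5.1 conflict on where to count an adverse event that starts under blinded treatment and ends open-label drug, and neither says how to count one that turns severe or serious after the switch

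*SAP*

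**What the plan says.** Two SAP sections decide the phase of an AE.

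- **SAP 7.1** uses timing of occurrence and start date: "If an AE occurred in Blinded Treatment phase, this AE will be summarized under blinded treatment group", and for subjects who crossed over, "an AE will be summarized under OL treatment if this AE start date is on or after the first dose of OL treatment".
- **SAP 7.1.5.1** defines treatment-emergent AEs (TEAEs) separately for each phase. For a subject who took OL drug, the onset criterion makes an AE a blinded-phase TEAE if it began on or after the start of blinded drug and "before the OL Treatment phase study drug start date if OL Treatment phase study drug was taken". The OL definition has two alternatives: "TEAEs for the OL Treatment phase are defined as 1 or both of the following". The first is onset on or after the start of OL drug. The second does not depend on onset: "Any AEs leading to premature discontinuation of OL Treatment phase study drug".

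SAP 7.1.6.1 then counts subjects by treatment group, with rows for Grade 3 or higher, serious AEs and TEAEs leading to discontinuation. The discontinuation row refers to study drug without saying which phase's drug.

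On recording, Protocol 7.2.2 says: "For each episode, the highest grade attained should be reported". Protocol 7.3.1 has AEs followed until they resolve or stabilise, so follow-up can run across the change of phase.

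On crossover, Protocol 3.1 lets Week 10 non-responders from every arm enter the OL phase, with OL Day 1 normally within 14 days of the Week 10 visit. Protocol 5.3 gives all of them 300 mg.

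Laboratory abnormalities have their own OL rule in SAP 7.2.2.1: "values that increase at least 1 toxicity grade from OL baseline at any postbaseline time point". AEs have no counterpart.

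**The concern.** A subject can carry an ongoing AE from blinded placebo or 100 mg into OL 300 mg. What happens to that AE afterwards happens on a different treatment, yet the main placement rule looks only at when the AE began. Severity, seriousness or withdrawal that arose on 300 mg could then appear against placebo or 100 mg. That would raise the comparator's counts and, where the event is left out of the OL column, lower those for OL 300 mg.

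The direction matters in this trial. Protocol 1.4 names a theoretical risk that the drug's mechanism could worsen ulcerative colitis, and the subjects who cross over are those who did not respond by Week 10. Efficacy summaries (SAP 6.2.2, 6.3.2), numeric laboratory summaries (7.2.1), vital signs (7.3) and ECG (7.5) have all been dropped, so the AE tables are among the few by-arm results left.

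**Working it through.** The plan gives no figure for this point, so there is none to reproduce. The check applies the SAP's rules to three cases.

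**Common starting point.** A subject on blinded placebo or 100 mg has an AE with onset after the first blinded dose. It is ongoing at the first OL dose, and one AE record is kept with one start date.

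| What happens on OL 300 mg | SAP 7.1 | SAP 7.1.5.1 | Where it is counted |
|---|---|---|---|
| (a) Reaches Grade 3 or higher | Blinded | Blinded TEAE only | Blinded arm, Grade 3+ row |
| (b) Becomes serious | Blinded | Blinded TEAE only | Blinded arm, SAE row |
| (c) Leads to stopping OL drug | Blinded | Blinded TEAE by onset, and OL TEAE by the second OL criterion | Blinded, OL or both: not determined |

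**Cases (a) and (b).** Start date and onset both point to the blinded arm. Neither section asks when the grade or the seriousness was reached. With one record at its highest grade, the blinded arm receives a status that was first reached on 300 mg.

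This depends on the single-record assumption. If the site opens a new record when the AE worsens, that record has an OL start date and both sections place it under OL. Protocol 7.2.2 fixes the grade per episode but does not say whether worsening after a change of treatment is a new episode. The Protocol's rule on worsening (7.1.1) covers preexisting events only. The eCRF completion guidelines, to which Protocol 7.3.2 refers, are not in the documents.

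**Case (c).** This needs no assumption about how sites handle worsening. Section 7.1 gives a blinded-onset AE to the blinded arm. Section 7.1.5.1 makes it a TEAE of both phases. Because the discontinuation row in 7.1.6.1 names no phase, a blinded TEAE by onset that later led to stopping OL drug literally qualifies for the blinded arm's discontinuation row. The SAP does not say which section governs.

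**Size of one event.** The SAP reports 19 subjects enrolled (1.2), randomised 1:1:1, so 19 / 3 = 6.3 per arm on average. Actual arm sizes are not given. Taking 5 to 7 per blinded arm as an assumption, one subject moves an arm's percentage by 100 / n:

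- n = 5: 100 / 5 = 20.0 points
- n = 6: 100 / 6 = 16.7 points
- n = 7: 100 / 7 = 14.3 points

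The matching change in the OL column cannot be computed, because the number entering the OL phase is not given. Nor is the number of AEs ongoing at the first OL dose.

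**The case against.** The strongest reply is that assignment by onset is a stated and workable rule, that the SAP already treats an AE ending OL drug as an OL TEAE, and that little can go wrong in a study of 19 subjects with no testing (SAP 3.5) and by-subject listings of all AEs, SAEs, deaths and discontinuation AEs (7.1.6.1). Much of this stands, and it rules out three stronger readings.

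- A reader might infer that treatment-ending AEs simply go to the blinded arm and vanish from OL. Section 7.1.5.1 does not support that: its second OL criterion captures them. The defect is that 7.1 and 7.1.5.1 are not reconciled.
- A reader might take "the most severe grade will be used for those AEs that occurred more than once in an individual subject during the study" to mean that a study-wide maximum grade feeds the blinded arm. That sentence governs summaries by severity grade, and 7.1.6.1 lists no maximum-grade table. Its Grade 2+ and Grade 3+ rows only need at least one qualifying TEAE, and a recurrence starting in the OL phase is already placed there.
- A reader might project how many records the planned 180-subject design would misplace. The documents give no crossover rate and no rate of worsening, so no such count is supportable.

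The laboratory comparison also has limits. Laboratory values are dated at each visit, whereas the history of an AE's grade may not be, so a full re-basing of AEs may not be possible.

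The objection does not remove the conflict for AEs that end OL drug. The listings are only a partial safeguard: SAP Section 3 shows subjects under their randomised or initially assigned group, and a record with one start date and one highest grade does not reveal that the worsening came after the switch. SAP 3.2 groups data collected in the OL phase by treatment received across both phases, but does not say whether a grade or seriousness reached then, for an AE that began earlier, is such data.

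**Conclusion.** The point holds in a limited form. For an AE with onset on blinded placebo or 100 mg that ends OL 300 mg treatment, the SAP supports tabulation in the blinded arm, the OL group or both, so a discontinuation of OL 300 mg can be credited to a comparator. For an AE that becomes Grade 3 or higher, or serious, only after the first OL dose, the blinded arm takes the count if the site keeps one record. That second part is conditional on recording practice which the documents do not show.

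For subjects who were already on blinded 300 mg, the phase may be wrong but the dose is not.

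The effect is confined to descriptive safety tables. One event shifts an arm's rate by about 14 to 20 percentage points if arms have 5 to 7 subjects (assumed), which is what any single event does in arms that small. Nothing in the documents shows that any AE was in fact ongoing at the switch.

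**What to change.** 1. **Align the rules.** Amend SAP 7.1 so that the phase of an AE follows the phase-specific TEAE definitions in 7.1.5.1.
2. **Tie discontinuation to the drug stopped.** In 7.1.6.1, count each discontinuation row only for that phase's drug. An AE that ends OL drug is then tabulated as a discontinuation under OL and not under the blinded arm.
3. **Review AEs ongoing at the first OL dose.** Where the data show that Grade 3 or higher, or seriousness, was first reached after that dose, tabulate that status under OL. Where the data cannot show it, flag the event with a footnote.

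The cost is a few SAP sentences and a review of ongoing AEs in at most 19 subjects. The SAP is signed, but its Section 1 already provides for later changes to be documented in the synoptic study report. The review uses whatever dated information exists and does not depend on new grade histories from sites. The downside is that some episodes will appear in both phases, which the table footnotes should state.

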7.1.1. Adverse Event Dictionary

Clinical and laboratory AEs will be coded using the current version of Medical Dictionary for Regulatory Activities (MedDRA). System organ class (SOC), high-level group term (HLGT), high-level term (HLT), preferred term (PT), and lower-level term (LLT) will be provided in the AE dataset.

7.1.2. Adverse Event Severity

Adverse events are graded by the investigator as Grade 1, 2, 3, 4, or 5 according to toxicity criteria specified in the protocol. The severity grade of events for which the investigator did not record severity will be categorized as “missing” for tabular summaries and data listings. The missing category will be listed last in summary presentation.

7.1.3. Relationship of Adverse Events to Study Drug

Related AEs are those for which the investigator selected “Related” on the AE CRF to the question of “Related to Study Treatment.” Relatedness will always default to the investigator’s choice, not that of the medical monitor. Events for which the investigator did not record relationship to study drug will be considered related to study drug for summary purposes. However, by-subject data listings will show the relationship as missing.

7.1.4. Serious Adverse Events

Serious adverse events (SAEs) will be identified and captured as SAEs if the AEs met the definitions of SAEs that were specified in the study protocol. SAEs captured and stored in the clinical database will be reconciled with the SAE database from the Gilead Drug Safety and Public Health Department before data finalization.

7.1.5. Treatment-Emergent Adverse Events

7.1.5.1. Definition of Treatment-Emergent Adverse Events

Treatment-emergent adverse events (TEAEs) for the Blinded Treatment phase are defined as 1 or both of the following:

- Any AEs with an onset date on or after the Blinded Treatment phase study drug start date and no later than 30 days after permanent discontinuation of the Blinded Treatment phase study drug if no OL Treatment phase study drug was taken, OR any AEs with an onset date on or after the Blinded Treatment phase study drug start date and before the OL Treatment phase study drug start date if OL Treatment phase study drug was taken.
- Any AEs leading to premature discontinuation of Blinded Treatment phase study drug.

TEAEs for the OL Treatment phase are defined as 1 or both of the following:

- Any AEs with an onset date on or after the OL Treatment phase study drug start date and no later than 30 days after permanent discontinuation of the OL Treatment phase study drug.
- Any AEs leading to premature discontinuation of OL Treatment phase study drug.

7.1.5.2. Incomplete Dates

If the onset date of the AE is incomplete and the AE stop date is not prior to the first dosing date of study drug, then the month and year (or year alone if month is not recorded) of onset determine whether an AE is treatment emergent. The event is considered treatment emergent if both of the following 2 criteria are met:

- The AE onset is the same as or after the month and year (or year) of the first dosing date of study drug, and
- The AE onset date is the same as or before the month and year (or year) of the date corresponding to 30 days after the date of the last dose of study drug

An AE with completely missing onset and stop dates, or with the onset date missing and a stop date later than the first dosing date of study drug, will be considered to be treatment emergent. In addition, an AE with the onset date missing and incomplete stop date with the same or later month and year (or year alone if month is not recorded) as the first dosing date of study drug will be considered treatment emergent.

7.1.6. Summaries of Adverse Events and Deaths

Treatment-emergent AEs will be summarized based on the Safety Analysis Set.

7.1.6.1. Summaries of AE Incidence in Combined Severity Grade Subsets

A brief, high-level summary of the number and percentage of subjects who experienced at least 1 TEAE in the categories described below will be provided by treatment group. All deaths observed in the study will also be included in this summary.

- TEAE
- TEAEs with Grade 3 or higher
- TEAEs with Grade 2 or higher
- TE treatment-related AEs
- TE treatment-related AEs with Grade 3 or higher
- TE SAEs
- TE treatment-related SAEs
- TEAEs leading to premature discontinuation of study drug

The number and percentage of subjects who experienced at least 1 TEAE will be provided and summarized by PT and treatment group. For the other AE categories described below, summaries will be provided by SOC, PT, and treatment group:

- TE treatment-related AEs
- TE SAEs
- TEAEs leading to premature discontinuation of study drug

Multiple events will be counted only once per subject in each summary. Adverse events will be summarized and listed first in alphabetic order of SOC within each SOC (if applicable), and then by PT in descending order of total frequency within each SOC. For summaries by severity grade, the most severe grade will be used for those AEs that occurred more than once in an individual subject during the study.

Data listings will be provided for the following:

- All AEs, indicating whether the event is treatment emergent
- All SAEs
- All Deaths
- All AEs leading to premature discontinuation of study drug

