3.1. Study Design

A schematic of this study design is provided in Figure 3-1.

Figure 3-1.

Abbreviations: QD once daily

This study includes:

- Screening period (Days -30 to -1)
- Baseline/Randomization (Day 1)

Approximately 180 subjects who meet protocol eligibility criteria will be randomized in a 1:1:1 ratio to 1 of 3 treatment groups as follows:

Treatment group 1 (n = 60): GS-4875 300 mg once daily

Treatment group 2 (n = 60): GS-4875 100 mg once daily

Treatment group 3 (n = 60): Placebo once daily

Treatment assignments will be stratified according to the sum (≤ 6 or > 6) of 3 MCS subscores for Stool Frequency, Rectal Bleeding, and Endoscopic Findings at Screening.

- Blinded Treatment phase (Day 1 up to Week 50)

At Week 10 visit, all subjects will have an efficacy assessment.

- Until response can be assessed based on Week 10 results, subjects will continue on their current assigned study drug regimen. Subjects who achieve MCS Response (Section 2) based on results from Week 10 will continue in the Blinded Treatment phase. All subjects who do not achieve MCS Response will discontinue the Blinded Treatment phase and have the option to enter the open-label (OL) phase.
- Subjects with insufficient data to assess MCS Response will discontinue study drug and are not eligible for the OL Treatment phase.

- Open-label Treatment phase (OL Day 1 up to OL Week 50)

OL Day 1 visit should occur within 14 days of Blinded Treatment phase Week 10 visit unless otherwise approved by the medical monitor.

At OL Week 10 visit, all subjects will have an efficacy assessment.

- Until response can be assessed based on Week 10 results, subjects will continue OL study drug. Subjects who achieve MCS Response (Section 2) based on results from OL Week 10 will continue in the OL Treatment phase. All subjects who do not achieve MCS Response will discontinue study drug.
- Subjects with insufficient data to assess MCS Response will discontinue study drug.

- Gilead Data Review Committee

After approximately 90 subjects complete the Week 10 visit or discontinue from the study prior to Week 10, the GDRC will review endpoint data for potential study termination due to lack of efficacy.

- Unblinding

The study will be unblinded when all randomized subjects (approximately 180) have either completed the Blinded Treatment phase Week 10 visit and all associated efficacy and safety assessments, or discontinued the study before Week 10.

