After study-wide unblinding, subjects who were receiving placebo will discontinue study drug. Subjects should attend the clinic at their next scheduled study visit or earlier, and undergo the ET assessments followed by the Posttreatment (PTx) assessments 30 days after the last dose of study drug.

After study-wide unblinding, subjects who were receiving blinded GS-4875 300 mg and GS-4875 100 mg will remain on the same dose. These subjects will continue the Blinded Treatment phase visit schedule up to Week 50.

- Posttreatment (PTx) Assessments

Subjects who discontinue study drug will return 30 days after the last dose for PTx assessments.

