1.2. Study Design

This is a Phase 2, blinded, randomized, placebo-controlled study evaluating the efficacy and safety of GS-4875 for the treatment of subjects with moderately to severely active ulcerative colitis (UC). Adult male or female subjects 18 years of age or older who have documented evidence of UC and previously demonstrated an inadequate response or loss of response to a TNF α inhibitor may be eligible for entry (refer to the protocol for complete inclusion and exclusion criteria).

Approximately 180 subjects who meet protocol eligibility criteria will be randomized in a 1:1:1 ratio to 1 of 3 treatment groups as follows:

Treatment group 1 (n = 60): GS-4875 300 mg once daily

Treatment group 2 (n = 60): GS-4875 100 mg once daily

[figure not shown]
Treatment group 3 (n = 60): Placebo once daily

Central randomization is used. Treatment assignments will be stratified according to the sum (≤ 6 or > 6) of 3 MCS subscores for Stool Frequency, Rectal Bleeding, and Endoscopic Findings at Screening.

The study was terminated after 19 subjects were enrolled in the study.

A schematic of this study design is provided in [Figure 1](#).

Figure 1. Study Schema

This study includes:

- Screening period (Days –30 to –1)
- Baseline/Randomization (Day 1)
- Blinded Treatment phase (Day 1 up to Week 50)
 - At Week 10 visit, all subjects will have an efficacy assessment.
 - Subjects who achieve MCS Response based on results from Week 10 will continue in the Blinded Treatment phase.
- Open-label Treatment phase (OL Day 1 up to OL Week 50)
 - All subjects who do not achieve MCS Response based on results from Week 10 will discontinue the Blinded Treatment phase and have the option to enter the OL Treatment phase.
 - At OL Week 10 visit, all subjects will have an efficacy assessment.
 - Subjects who achieve MCS Response based on results from OL Week 10 will continue in the OL Treatment phase. All subjects who do not achieve MCS Response will discontinue study drug.
- Posttreatment (PTx) Assessments

In the Blinded Treatment phase, randomized subjects may receive a maximum of 50 weeks of treatment. Subjects, who move to the OL Treatment phase, will have received 10 weeks of blinded treatment and may receive up to 50 weeks of OL treatment. Thus, total duration of treatment may be a maximum of 60 weeks.

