7.2.2.2. Summaries of Laboratory Abnormalities

Laboratory data that are categorical will be summarized using the number and percentage of subjects in the study with the given response at baseline and each scheduled postbaseline time point for both Blinded Treatment phase and OL Treatment phase.

The following summary (number and percentage of subjects) for treatment-emergent laboratory abnormalities will be provided by laboratory test and treatment group; subjects will be categorized according to the most severe postbaseline abnormality grade for a given laboratory test:

- Graded laboratory abnormalities

For all summaries of laboratory abnormalities, the denominator is the number of subjects with nonmissing postbaseline values.

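### Blinded-phase adverse-event and laboratory percentages are crude, over a window whose length depends on Week 10 response and, in the final analysis, on arm

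*SAP*

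**What the plan says.** SAP 7.1.6.1 gives a "summary of the number and percentage of subjects who experienced at least 1 TEAE in the categories described below will be provided by treatment group", counting each subject once. SAP 7.1 sets the column: "If an AE occurred in Blinded Treatment phase, this AE will be summarized under blinded treatment group". The tables use the Safety Analysis Set, which SAP 3.2 groups by treatment actually received.

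SAP 7.1.5.1 sets two different ends to the blinded-phase window. It closes "no later than 30 days after permanent discontinuation of the Blinded Treatment phase study drug if no OL Treatment phase study drug was taken", but "before the OL Treatment phase study drug start date if OL Treatment phase study drug was taken".

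SAP 7.2.2.1 sets matching limits for laboratory abnormalities, and under SAP 7.2.2.2 "subjects will be categorized according to the most severe postbaseline abnormality grade for a given laboratory test".

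Protocol 3.1 decides who stays in the blinded phase: "All subjects who do not achieve MCS Response will discontinue the Blinded Treatment phase and have the option to enter the open-label (OL) phase". OL Day 1 should follow within 14 days of the Week 10 visit. Later, "After study-wide unblinding, subjects who were receiving placebo will discontinue study drug", whereas both GS-4875 groups keep their dose and follow the blinded-phase visit schedule to Week 50.

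Neither document specifies an adverse-event table limited to Week 10 or an exposure-adjusted rate. SAP 4.2.1 tabulates exposure by treatment group and phase, as a separate output.

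**The concern.** A crude percentage of subjects with at least one event rises with time observed. All groups share the same nominal window only up to Week 10. After that, time in the blinded-phase column depends on MCS Response, which is a post-randomization outcome, and in the final analysis on which arm is stopped at unblinding. Side-by-side percentages then mix the event rate with the length of observation.

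Safety is a stated secondary objective (SAP 1.1.2). The SAP drops the efficacy summaries (6.2.2, 6.3.2), numeric laboratory summaries (7.2.1), vital signs (7.3) and ECG (7.5). The adverse-event and graded-laboratory tables are the main between-group outcome tables left. With no test or interval attached, readers will take the percentages at face value.

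**Working it through.** The plan states no figure on this point. Its one design calculation, power of about 75%, reproduces at 75.1% by exact enumeration of Fisher's test and is not involved here.

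**1. Window length, from the documents**
- Non-responder entering OL: Week 10 visit plus 0 to 14 days, so about 10 to 12 weeks.
- Non-responder declining OL: last dose plus 30 days, so about 10 + 4.3 = 14.3 weeks if dosing stops at Week 10.
- GS-4875 responder: 50 weeks + 30/7 = 54.3 weeks at most.
- Placebo responder: the same limit, or unblinding plus 30 days if earlier.

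**2. Laboratory opportunities, from SAP Appendix 1**
A responder who completes has 14 scheduled postbaseline hematology and chemistry draws (Weeks 2 to 50) plus the posttreatment draw. A non-responder entering OL has 4 (Weeks 2, 4, 6, 10), plus OL Day 1 if drawn before dosing. More draws give more chances of a worse worst grade. This needs no assumed rate.

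**3. Equal hazard in both arms, fixed stopping times**
The documents give no MCS response rate, adverse-event rate or unblinding time per subject, so these are assumed. With response r, weekly hazard h and responder window T:

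P = r(1 − exp(−hT)) + (1 − r)(1 − exp(−12h))

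At h = 0.02 the pieces are 1 − exp(−0.02 × 54.3) = 0.662 for a full-course responder, 1 − exp(−0.24) = 0.213 for a non-responder, and 1 − exp(−0.02 × 34.3) = 0.496 for a placebo responder stopped at Week 30.

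| Response, GS-4875 / placebo | Placebo responders stop at | GS-4875 | Placebo | Difference |
|---|---|---|---|---|
| 50% / 50% | Week 50 | 43.8% | 43.8% | 0 |
| 50% / 50% | Week 30 | 43.8% | 35.5% | +8.3 points |
| 50% / 50% | Week 14 | 43.8% | 26.0% | +17.8 points |
| 40% / 20% | Week 50 | 39.3% | 30.3% | +9.0 points |
| 40% / 20% | Week 30 | 39.3% | 27.0% | +12.3 points |

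With h from 0.01 to 0.05, response 30–60% on GS-4875 and 20–50% on placebo (placebo never the higher), the range is 0 to +26 points.

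**4. Equal rate, planned trial with uniform accrual**
Assume 1 first event per patient-year, response 45% versus 20%, accrual over 52 weeks, non-responders observed for 11 weeks, and every GS-4875 responder staying to Week 50. A placebo subject entering at week t is dosed for d = min(50, 62 − t) weeks. Mean d = (12/52) × 50 + (40/52) × 30 = 34.6 weeks, or 38.9 with the 30 days.
- Mean time on GS-4875: 0.55 × 11 + 0.45 × 54.3 = 30.5 weeks.
- Mean time on placebo: 0.80 × 11 + 0.20 × 38.9 = 16.6 weeks.
- Percentage with an event: 39.6% versus 25.5%, ratio 1.56, with no drug effect.

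Variations:
- Accrual 52–104 weeks, rate 0.5–2 per year, response 45/20% or 40/25%: ratio 1.21 to 1.68.
- Equal 30% response, placebo withdrawal alone: 1.04 to 1.19.
- All arms stopped together (52-week accrual, 1 per year): 33.5% versus 25.5%, ratio 1.31. With equal response it is 1.00.
- Response 15–20% on GS-4875 and 30% on placebo (104-week accrual, 1 per year): 0.84 to 0.92.

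**5. Scale for the actual trial**
19/3 is about 6 per arm, so one subject is 1/6 = 16.7 points. The 14.1-point gap in step 4 is 0.141 × 6 = 0.8 of a subject. An observed 3/6 has an exact 95% interval of 11.8% to 88.2%.

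**6. With a Week 10 limit**
Ignoring earlier dropout, equal hazards give 9.5%, 18.1% and 39.3% in every arm at h = 0.01, 0.02 and 0.05.

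**The case against.** The strongest reply is that this SAP supports a synoptic report on 19 subjects (SAP 1, 1.2) with no testing (SAP 3.5). Exposure by arm and phase, disposition after Week 10 and a full adverse-event listing are all provided, so a reader can set every event against exposure. That stands and limits the practical weight. It does not correct the percentages themselves.

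The arm-dependent part is also uncertain here:
- At the primary analysis (SAP 2.2), placebo has not yet been stopped under the unblinding rule. Only the final analysis (SAP 2.3) is affected.
- SAP 1 says enrollment was terminated, and SAP 1.2 says the study was. Protocol 6.13.3 lists discontinuation of the study at the sponsor's request among the reasons for stopping study drug. If that ended all arms together, only the response-dependent part would remain. The documents do not settle this.
- Protocol 6.14 describes supply after unblinding as open-label, while Protocol 3.1 keeps these subjects on the blinded-phase schedule. Placing that time in the blinded column is the better-supported reading, but the SAP does not say so.

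The illustrations also keep every GS-4875 responder to Week 50, despite the stopping rules in Protocol 6.13.3. Allowing early stopping would shrink them.

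A reader might infer that the tables are bound to show excess harm on GS-4875. The documents do not support that. Protocol 1.4 allows for no treatment effect or worsening of disease, and the same formula gives ratios below 1 when placebo response is sufficiently higher.

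**Conclusion.** The point holds as a defect of presentation. The crude percentages and worst grades are taken over windows that depend on Week 10 response in either analysis and, under the unblinding rule, also on arm in the final one. Equal true rates need not give equal percentages. The direction depends on relative response and on when placebo stops. There is no distortion if both are equal.

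The structure follows from the text alone. The size does not, since response, event rate and accrual are all assumed. Ratios of about 1.0 to 1.7 describe the planned 180-subject trial under those assumptions, with response on GS-4875 at least that on placebo. It would be wrong to read a 1.5-fold spurious excess into the report on these 19 subjects, where the shift is about one subject per arm. The change is still worth making because it is cheap and these are the main comparative tables left.

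**What to change.** In SAP 7.1.6.1 and 7.2.2.2, limit the between-group adverse-event and graded-laboratory tables to first dose through the Week 10 visit date (Day 71 if there is no Week 10 visit), and before any OL dose. Response is determined only from Week 10 results, so this cut cannot depend on it. Ending at the earlier of OL Day 1 or Day 85, the upper limit of the SAP's Week 10 analysis window, would not achieve this. Responders would run to Day 85 while non-responders stopped at OL Day 1, leaving a gap of up to about 85 − 71 = 14 days.

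Show later blinded-phase events in a separate table with subject-weeks at risk. Flag events after study-wide unblinding, and state which column that time belongs to.

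The cost is SAP wording, a date cut on existing data and one extra descriptive table. Any person-time rates would be imprecise at about 6 subjects per arm and should be labelled so. No dose, schedule or clinical rule changes.
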